### 10.5.2 Clinical Safety Labs, Vital Signs, and Electrocardiograms

Baseline for clinical safety labs, vital signs, and ECGs will be defined as the last result obtained before the dose of study product. Clinical safety labs, vital signs, and ECGs results and changes from baseline will be summarized by treatment arm and visit. Clinical safety labs and vital signs will be graded ([Appendix B](#)) and summarized by severity, treatment arm, and visit. If triplicate ECG measurements were performed at the same visit, then baseline is the mean value of the measurements for the visit closest to, but before, administration of study drug. Similarly, for analyses of change from baseline, mean values will be used in the case of replicate measurements at a single visit post-baseline.

Treatment-emergent abnormal laboratory test results will be identified. Treatment-emergent abnormal laboratory tests are tests for which the result was not graded as mild or worse at baseline but graded as mild or worse after dosing. Laboratory tests graded as mild at baseline,

but moderate or worse any time after dosing will also be regarded as treatment-emergent abnormal laboratory test results.

ECG measurements will include heart rate, RR interval, QT interval, QTcF interval, PR interval, and QRS duration. Baseline for ECG measurements is defined per protocol as the value pre-dosing on Day 1. Change from baseline will be summarized descriptively by regimen at each scheduled evaluation. QTc results will be summarized categorically according to the ICH Guideline E14 “Clinical Evaluation of QT/QTc Interval Prolongation and Proarrhythmic Potential for Non-Antiarrhythmic Drugs” (October 2005).

- QTcF >450 ms;
- QTcF >450 ms, males only;
- QTcF >470 ms, females only;
- QTcF >480 ms;
- QTcF >500 ms;
- QTcF increases from baseline by at least 30 ms but less than 60 ms;
- QTcF increases from baseline by at least 60 ms.

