## Appendix B. VT-1598 TOXICITY GRADING CRITERIA FOR NORMAL HUMAN SUBJECTS

Adverse Events*	Mild (Grade 1)	Moderate (Grade 2)	Severe (Grade 3)
Laboratory Adverse Events* (Blood, Serum or Plasma)			
Sodium (hyponatremia) – mEq/L	131-132	129-130	<129
Sodium (hypernatremia) – mEq/L	144-145	146-147	>147
Potassium (hyperkalemia) – mEq/L	5.2 – 5.4	5.5 – 5.6	>5.6
Potassium (hypokalemia) – mEq/L	3.2-3.4	3.0 – 3.1	<3.0
Phosphorus – mg/dL (Hypo)	2.3 – 2.4	2.1 – 2.2	≤2.0
Phosphorus – mg/dL (Hyper)	N/A	N/A	N/A
Magnesium – mg/dL	1.3-1.5	1.1-1.2	<1.1
Gamma- Glutamyl Transferase (GGT) – Male – U/L	N/A	N/A	N/A
Gamma- Glutamyl Transferase (GGT) – female – U/L	N/A	N/A	N/A
Glucose (hypoglycemia) – mg/dL	65 – 69	55 – 64	<55
Glucose (hyperglycemia) – mg/dL Fasting	106 – 125	126 – 200	>200
Blood Urea Nitrogen – mg/dL	21-26	27 – 31	> 31
Creatinine (Male) – mg/dL	1.3 – 2.0	2.1-2.3	>2.3
Creatinine (Female) – mg/dL	1.0 – 1.7	1.8 – 2.0	>2.0
Calcium (hypocalcemia) – mg/dL	8.0 – <LLN	7.5 – 7.9	<7.5

Adverse Events*	Mild (Grade 1)	Moderate (Grade 2)	Severe (Grade 3)
Calcium (hypercalcemia) – mg/dL	10.4-10.8	10.9-11.4	>11.4
Chloride – mEq/L	N/A	N/A	N/A
CPKt-U/L (Male)	1.1 - ≤ 1.5 x ULN	>1.5 - ≤ 3.0 x ULN	>3.0 ULN or higher
CPKt – U/L(Female)	1.1 - ≤ 1.5 x ULN	>1.5 - ≤ 3.0 x ULN	>3.0 ULN or higher
A.M. Cortisol (serum, drawn prior to 10 a.m.) – ug/dL	1-10% below LLN	10-25 % below LLN	>25% below LLN with or without symptoms
Albumin (hypoalbuminemia) – g/dL	2.8 – 3.4	2.5 – 2.7	< 2.5
AST – U/L	1.1 - ≤ 2.5 x ULN	>2.5 - ≤ 5.0 x ULN	>5.0 x ULN or higher
ALT – U/L	1.1 - ≤ 2.5 x ULN	>2.5 - ≤ 5.0 x ULN	>5.00 x ULN or higher
Total Bilirubin (serum) – mg/dL	1.1 - ≤ 1.25 x ULN	>1.25 - ≤ 1.50 x ULN	>1.50 x ULN or higher
Direct Bilirubin – mg/dL	1.1 - ≤ 1.25 x ULN	>1.25 - ≤ 1.50 x ULN	>1.50 x ULN or higher
Indirect Bilirubin – mg/dL	1.1 - ≤ 1.25 x ULN	>1.25 - ≤ 1.50 x ULN	>1.50 x ULN or higher
Amylase – U/L	1.1 - ≤ 1.5 x ULN	>1.5 - ≤ 2.0 x ULN	>2.0 x ULN or higher
Lipase – U/L	1.1 - ≤ 1.5 x ULN	>1.5 - ≤ 2.0 x ULN	>2.0 x ULN or higher
Hemoglobin (Male) – g/dL	11.2 - 12.2	10.0 – 11.1	<10.0
Hemoglobin (Female) – g/dL	9.8 - 10.8	8.5 - 9.7	<8.5
WBC Increase – cell/mm 	10,001– 15,000	15,001 – 20,000	> 20,000
WBC Increase – cell/mm  (African America Males)	9,001 – 14, 000	14,001 – 19, 000	>19,000
WBC Increase – cell/mm  (African American Females)	11,001 – 15,000	15,001 – 20,000	>20,000

Adverse Events*	Mild (Grade 1)	Moderate (Grade 2)	Severe (Grade 3)

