WBC Decrease – cell/mm 	2,500– 3,999	1,500 – 2,499	< 1,500
WBC Decrease – cell/mm  (African American Males)	2,200 – 2,499	1,200 – 2,199	<1,200
WBC Decrease – cell/mm  (African American Females)	2,200 – 2,499	1,500 – 2,199	<1,500
Neutrophils Decrease – cell/mm 	1,300 – <1,699	1,000 – 1,299	< 1,000
Neutrophils Decrease – cell/mm  (African American Males)	1,000 – 1,299	800 - 999	<800
Neutrophils Decrease – cell/mm  (African American Females)	1,100 – 1,299	1,000 – 1,099	<1,000
Platelets Decreased - cell/mm 	120,000 – <150,000	100,000 – 119,999	<100,000
PT (prothrombin time) – seconds	11.6 – 12.6	12.7 – 13.7	>13.7
PT INR (Prothrombin INR)	1.2-1.4	1.5-1.9	2.0 or higher
PTT (partial thromboplastin time) –seconds	30.1 – 36.8	36.9 – 43.6	>43.6
Total Protein – g/dL	5.5 - 5.9	5.0 - 5.4	<5.0
Alkaline phosphatase – IU/L (Male)	1.1 - ≤ 2.0 x ULN	>2.0 - ≤ 3.0 x ULN	>3.0 x ULN or higher
Alkaline phosphatase – IU/L (Female)	1.1 - ≤ 2.0 x ULN	>2.0 - ≤ 3.0 x ULN	>3.0 x ULN or higher
Hematocrit (Male) - %	33.0 -36.1	29.8 - 32.9	< 29.8
Hematocrit (Female) - %	29.5 - 32.6	26.0 – 29.4	< 26.0
RBC (Male) – x 10  /uL	3.9 - 4.1	3.4 - 3.8	< 3.4

Adverse Events*	Mild (Grade 1)	Moderate (Grade 2)	Severe (Grade 3)
RBC (Female) – x 10  /uL	3.5 - 3.7	3.0 - 3.4	< 3.0
Lymphocytes - cell/mm  decrease	600- 799	500 – 599	< 500
Monocytes – cell/mm  increase	1001-2000	2001-3000	>3000
Eosinophils - cell/mm  increase	871 - 950	951 - 1700	>1700
Basophils - cell/mm  increase	101 - 300	301 - 800	> 800
High Density Lipoproteins (HDL) Male – mg/dL	N/A	N/A	N/A
High Density Lipoproteins (HDL) Female – mg/dL	N/A	N/A	N/A
Total Carbon Dioxide – mEq/L	N/A	N/A	N/A
Total Cholesterol – mg/dL	N/A	N/A	N/A
Low Density Lipoprotein Cholesterol, Direct – mg/dL	N/A	N/A	N/A
Triglycerides – mg/dL	N/A	N/A	N/A
Laboratory Adverse Events* (Urine)			
Protein	1+	2+	>2+
Glucose	1+	2+	>2+
Blood (microscopic) - red blood cells per high power field (rbc/hpf)**	3-10**	11-50**	>50 and/or gross blood**

\*Abnormal laboratory values, performed as part of hematology, chemistry panel, or urinalysis but not listed in Appendix B, VT-1598 TOXICITY GRADING CRITERIA FOR NORMAL HUMAN SUBJECTS, will be evaluated by the study clinicians, recorded in the source document and, if clinically significant, considered AEs and graded according to the criterion described in [Section 8.1](#).

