4.5. Safety and Pharmacokinetic Variables

The following section describes the safety and PK endpoints of the study. As this study is a Phase 1 clinical trial in healthy adult subjects, there will be no assessment of drug efficacy. For a detailed schedule of study procedures refer to [Table 2](#). Refer to Section 3 for a list of the primary and secondary objectives and endpoints. For definitions of baseline for safety endpoints, refer to Section 3.3.4.

Incidence, relatedness, and severity of treatment-emergent AEs and SAEs will be recorded from the time of dosing to the final visit on the appropriate eCRF. All AEs will be graded for severity and the relationship to the study product by a trained and qualified member of the study team as described in Sections 8.1 and 8.2 of the study protocol v5.0. AEs and SAEs are defined in Sections 8.1 and 8.2 of the study protocol v5.0.

Clinical AEs will be graded using the toxicity grading scales in [Table 3](#).

Clinical laboratory results, VS, and ECG results will be assessed using the toxicity grading scales in [Table 4](#), [Table 5](#), and [Table 6](#), respectively.

In addition to AEs, the following safety endpoints will be assessed according to the study procedure listed in [Table 2](#):

- CHEM, HEM, and COAG clinical laboratory result safety parameters:
 - The results will be graded according to the toxicity grading criteria in [Table 4](#).
 - The following parameters will be measured:
 - CHEM parameters: albumin, glucose, blood urea nitrogen, potassium, calcium, sodium, chloride, total protein, creatinine, triglycerides, total cholesterol, low-density lipoprotein cholesterol (LDL), high-density lipoprotein cholesterol (HDL), total carbon dioxide, creatine phosphokinase, phosphorus, alkaline phosphatase, AST, ALT, total bilirubin, direct bilirubin, magnesium, gamma-glutamyl transferase (GGT), and serum cortisol.
 - HEM parameters: hemoglobin, hematocrit, differential white blood cell count (lymphocytes, neutrophils, monocytes, eosinophils, basophils), platelet count, red blood cell count (RBC), and total white blood cell count (WBC).

- COAG parameters: Prothrombin time, Activated partial thromboplastin time (PTT), and international normalized ratio.

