9.6. Clinical Laboratory Evaluations

Toxicity grading criteria for clinical laboratory results can be found in [Table 4](#). Unscheduled clinical laboratory evaluations will be included in listings of all clinical laboratory results, but excluded from tabular and graphical summaries by timepoint, except when calculating the maximum severity post baseline. Any pre-existing abnormal lab results at Screening and Baseline will be graded and presented in listings but will not be reported as an AE unless it is treatment-emergent (i.e. severity worsens after dosing). Clinical laboratory parameters that have grading criteria for both decreases (result lower than normal range) and increases (result higher than normal range) will be summarized separately by direction. Descriptions of each clinical laboratory summary are described below:

The following laboratory parameters will be presented (in order):

- CHEM: albumin, glucose, blood urea nitrogen, potassium, calcium, sodium, chloride, total protein, creatinine, triglycerides, total cholesterol, LDL cholesterol, HDL cholesterol, total carbon dioxide, creatine phosphokinase, phosphorus, magnesium, GGT, alkaline phosphatase, AST, ALT, total bilirubin, direct bilirubin, and serum cortisol.
- HEM: hemoglobin, hematocrit, lymphocytes, neutrophils, monocytes, eosinophils, basophils, platelet count, RBC, and WBC.
- COAG: prothrombin time, PTT, and international normalized ratio.

- UA: specific gravity by dipstick, pH by dipstick, occult blood by dipstick, leukocyte esterase by dipstick, RBC by complete UA, and WBC by complete UA (microscopic tests to be completed if dipstick urinalysis is abnormal). If microscopic results were obtained in the absence of an abnormal dipstick result (or without dipstick tests being done), results of the complete urinalysis or microscopy will still be summarized.

All safety laboratory results, severity, and change from baseline will be listed for each subject by Dose Group and timepoint. Abnormal laboratory results (laboratory results outside the normal range defined in the MOP) will be presented. Abnormal laboratory results that do not have toxicity grading ranges defined in the protocol will not have severity indicated in tables and listings of abnormal laboratory results, except as “ONR” (out of normal range).

- All CHEM results, including unscheduled visits, will be presented in [Listing 12](#). Abnormal results will be presented in [Table 23](#).

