Parameter ^a	Direction	Mild (Grade 1)	Moderate (Grade 2)	Severe (Grade 3)
WBC (African American Females) - cell/mm ³	Increase	11,001 – 15,000	15,001 – 20,000	>20,000
WBC - cell/mm ³	Decrease	2,500 – 3,999	1,500 – 2,499	< 1,500
WBC (African American Males) - cell/mm ³	Decrease	2,200 – 2,499	1,200 – 2,199	<1,200
WBC (African American Females) - cell/mm ³	Decrease	2,200 – 2,499	1,500 – 2,199	<1,500
Neutrophils - cell/mm ³	Decrease	1,300 – <1,699	1,000 – 1,299	< 1,000
Neutrophils (African American Males) - cell/mm ³	Decrease	1,000 – 1,299	800 - 999	<800
Neutrophils (African American Females) - cell/mm ³	Decrease	1,100 – 1,299	1,000 – 1,099	<1,000
Platelets - cell/mm ³	Decrease	120,000 – <150,000	100,000 – 119,999	<100,000
Prothrombin time - seconds	Increase	11.6 – 12.6	12.7 – 13.7	>13.7
Prothrombin INR	Increase	1.2-1.4	1.5-1.9	2.0 or higher
PTT (partial thromboplastin time) - seconds	Increase	30.1 – 36.8	36.9 – 43.6	>43.6
Total Protein - g/dL	Decrease	5.5 - 5.9	5.0 - 5.4	<5.0
Alkaline phosphatase (Male) - IU/L	Increase	131-260	264-390	> 390.1
Alkaline phosphatase (Female) - IU/L	Increase	106-210	211-315	> 315.1
Hematocrit (Male) - %	Decrease	33.0 -36.1	29.8 - 32.9	< 29.8
Hematocrit (Female) - %	Decrease	29.5 - 32.6	26.0 – 29.4	< 26.0
RBC (Male) - 10 ⁶ /uL	Decrease	3.9 - 4.1	3.4 - 3.8	< 3.4
RBC (Female) - 10 ⁶ /uL	Decrease	3.5 - 3.7	3.0 - 3.4	< 3.0
Lymphocytes - cell/mm ³	Decrease	600- 799	500 – 599	< 500
Monocytes - cell/mm ³	Increase	1001-2000	2001-3000	>3000
Eosinophils - cell/mm ³	Increase	871 - 950	951 - 1700	>1700
Basophils - cell/mm ³	Increase	101 - 300	301 - 800	> 800
High Density Lipoproteins (HDL) (Male) - mg/dL	N/A	N/A	N/A	N/A
High Density Lipoproteins (HDL) (Female) - mg/dL	N/A	N/A	N/A	N/A
Total Carbon Dioxide - mEq/L	N/A	N/A	N/A	N/A
Total Cholesterol - mg/dL	N/A	N/A	N/A	N/A
Low Density Lipoprotein Cholesterol, Direct - mg/dL	N/A	N/A	N/A	N/A
Triglycerides - mg/dL	N/A	N/A	N/A	N/A
Protein*	Increase	1+	2+	>2+
Glucose*	Increase	1+	2+	>2+
Blood (microscopic) - red blood cells per high power field - rbc/hpf* °	Increase	3-10	11-50	>50 and/or gross blood

^a Laboratory tests without toxicity grading defined in the protocol have N/A in this table for grading ranges.

*Abnormal laboratory values, performed as part of hematology, chemistry panel, or urinalysis but not listed in Table 4, VT-1598

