14.3.4 Abnormal Laboratory Value Listings (by Subject)

Table 23: Listing of Abnormal Laboratory Results – Chemistry

[Implementation Note: This listing is included in the table shells document, as it is included in the body of the CSR. This listing includes all abnormal Chemistry results (laboratory results outside of the normal range defined in the protocol). Normal chemistry results for other parameters that occurred on the same visit as the abnormal result will not be listed. There is a separate, complete listing of all Chemistry results in Appendix 3. In the Laboratory Parameter column, indicate the units in parentheses after the parameter, e.g., Sodium (mEq/L). This listing is not color-coded, but the severity should be included in parentheses after the result, e.g., 133 (Mild). Results that are outside the normal range but not mild, moderate, or severe will have (ONR) as the severity included after the result. Results that meet grading criteria of mild, moderate, or severe but which are not treatment emergent (not worse than baseline, as described in Section 9.6) will be shown as “ONR”.

Sort order: Dose Group, Subject ID, Timepoint, and Parameter.

Dose Group order: 40 mg Fasted, 80 mg Fasted, 160 mg Fasted, 160 mg Fed, 320 mg Fasted, 640 mg Fasted, Placebo.

Parameter order: albumin, glucose, blood urea nitrogen, potassium, calcium, sodium, chloride, total protein, creatinine, triglycerides, total cholesterol, low-density lipoprotein, high-density lipoprotein, total carbon dioxide, creatine phosphokinase, phosphorus, alkaline phosphatase, aspartate aminotransferase, alanine aminotransferase, total bilirubin, direct bilirubin, magnesium, gamma-glutamyl transferase (GGT), serum cortisol]

Dose Group	Subject ID	Sex	Age (years)	Timepoint	Date of Assessment	Laboratory Parameter (Units)	Result (Severity)

Table 24: Listing of Abnormal Laboratory Results – Hematology

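### SAP Table 4 does not reproduce the protocol's alkaline phosphatase grades: Mild starts at about 1.01 × ULN instead of 1.1 × ULN, and male values of 261-263 IU/L have no grade

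*SAP*

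**What the plan says.** Protocol Section 10.5.2 says safety laboratory results are graded by Appendix B. The male ALP row there reads "Alkaline phosphatase – IU/L (Male) 1.1 - ≤ 2.0 x ULN >2.0 - ≤ 3.0 x ULN >3.0 x ULN or higher", and the female row has the same multiples.

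The SAP turns these multiples into IU/L in Appendix 1, Table 4. The male row is "Alkaline phosphatase (Male) - IU/L Increase 131-260 264-390 > 390.1". The female row is 106-210, 211-315 and >315.1.

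Table 4 is the operative scale. For chemistry, hematology and coagulation, SAP Section 4.5 states "The results will be graded according to the toxicity grading criteria in" Table 4. The table is meant to carry the protocol's grading, since its footnote a says "Laboratory tests without toxicity grading defined in the protocol have N/A in this table for grading ranges". The reference ranges are not in either document: SAP Section 9.6 describes abnormal results as "laboratory results outside the normal range defined in the MOP". SAP Section 15, which lists changes to planned analyses, mentions only the Tmax comparison.

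**The concern.** No single ULN reproduces either ALP row, and the male row leaves a hole between Mild and Moderate. Laboratory results are part of the primary safety endpoint, and Table 4 decides how each result is labelled and counted.

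Two things follow. First, an out-of-range value that falls in the hole drops out of the Mild/Moderate/Severe counts. The implementation note to SAP Table 23 says "Results that are outside the normal range but not mild, moderate, or severe will have (ONR) as the severity included after the result". Second, Protocol Section 10.5.2 defines a treatment-emergent abnormality by grade. It covers a test where "the result was not graded as mild or worse at baseline but graded as mild or worse after dosing", or one that goes from mild at baseline to moderate or worse. Wrong limits therefore change which ALP rises count as emergent.

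ALP also feeds the chemistry Any Parameter and Maximum Severity Post Baseline rows. With six active subjects per dose group, one misgraded subject moves a proportion by 1/6, about 17 percentage points.

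**Working it through.** **Inputs.** The multiples come from Protocol Appendix B and the limits in units from SAP Table 4. Neither document states the ULNs, so each is inferred as implied ULN = SAP limit ÷ Appendix B multiple.

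**Step 1: implied ULN for all 13 rows that convert ULN multiples.**

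| Row | Mild lower limit | Mild upper limit | Moderate upper limit |
|---|---|---|---|
| ALP male | 131/1.1 = **119.1** | 260/2.0 = 130 | 390/3.0 = 130 |
| ALP female | 106/1.1 = **96.4** | 210/2.0 = 105 | 315/3.0 = 105 |
| CPK male | 338.8/1.1 = 308 | 462/1.5 = 308 | 924/3.0 = 308 |
| CPK female | 211.2/1.1 = 192 | 288/1.5 = 192 | 576/3.0 = 192 |
| AST male | 44/1.1 = 40 | 100/2.5 = 40 | 200/5.0 = 40 |
| AST female | 35.2/1.1 = 32 | 80/2.5 = 32 | 160/5.0 = 32 |
| ALT male | 45.1/1.1 = 41 | 102.5/2.5 = 41 | 205/5.0 = 41 |
| ALT female | 36.3/1.1 = 33 | 82.5/2.5 = 33 | 165/5.0 = 33 |
| Total bilirubin | 1.32/1.1 = 1.2 | 1.50/1.25 = 1.2 | 1.80/1.5 = 1.2 |
| Direct bilirubin | 0.22/1.1 = 0.2 | 0.25/1.25 = 0.2 | 0.30/1.5 = 0.2 |
| Indirect bilirubin | 1.31/1.1 = 1.191 | 1.49/1.25 = 1.192 | 1.79/1.5 = 1.193 |
| Amylase | 162.8/1.1 = 148 | 222/1.5 = 148 | 296/2.0 = 148 |
| Lipase | 73.7/1.1 = 67 | 100.5/1.5 = 67 | 134/2.0 = 67 |

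Eleven rows give one ULN each, within rounding. Only the two ALP rows fail, and only at the Mild lower limit.

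**Step 2: where ALP Mild should start.** Male 1.1 × 130 = 143; female 1.1 × 105 = 115.5. The SAP starts at 131/130 = 1.008 × ULN and 106/105 = 1.010 × ULN, which is ULN + 1 in each sex.

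**Step 3: where male Moderate should start.** Above 2.0 × 130 = 260. The SAP starts at 264/130 = 2.03 × ULN, so 261-263 lies between the SAP's Mild and Moderate. The female row runs 210 to 211 and has no whole-number gap.

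**Step 4: grade every whole-number enzyme value on both scales.** The only disagreements are:

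| Values (IU/L) | Protocol | SAP | Number |
|---|---|---|---|
| Male 131-142 | none | Mild | 12 |
| Female 106-115 | none | Mild | 10 |
| Male 261-263 | Grade 2 | none | 3 |

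**Step 5: effect on emergence, two male examples.** A rise from 125 to 138 is ungraded throughout in the protocol but becomes treatment-emergent Mild in the SAP. A rise from 200 to 262 is Grade 1 to Grade 2, hence emergent, in the protocol; in the SAP it is Mild to no grade, printed as ONR.

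**Step 6: related slips that depend on reporting precision.** Appendix B grades total bilirubin as Moderate at ">1.25 - ≤ 1.50 x ULN". At the implied ULN of 1.2 that is above 1.50 to 1.80, but the SAP prints 1.60-1.80. This affects 0 values at one decimal and 9 values (1.51-1.59) at two decimals. The CPK Severe limits (>924.1 and >576.1) affect nothing at whole numbers and one value per sex at one decimal. The documents do not state the precision.

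**The case against.** The mismatch itself is not open to rebuttal; the case on the other side is that it matters little.

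- **Adverse events are graded separately.** Under Protocol Section 8.1.1 the investigator grades AEs with Appendix B. A male ALP of 262 recorded as an AE would still appear as Moderate in SAP Listing 11 and, if non-serious, in Table 22. The halting rules use those AEs. This stands, and it confines the effect to the laboratory result tables and labels.
- **The emergence effect is narrower than it looks.** Table 28 counts grades at baseline and after dosing with no emergence filter. The instruction to show non-emergent graded results as ONR is written for the by-subject listings, Tables 23-26. This also stands. A male rise from 138 to 250, for example, would be Mild at 250 in Table 28 on either scale; only its listing label would change. Such a subject should rarely exist, because 138 would be out of range without being Appendix B Grade 1, and exclusion criterion 6 excepts only Grade 1 values.
- **The size is small.** The hole is three whole numbers just above 2 × ULN, in screened healthy adults after a single dose. The low Mild floor over-grades active and placebo alike. Raw values, changes from baseline and abnormal-high counts remain visible. All true, but a severity scale should not contain a hole, and small groups make single misgradings visible.
- **The ULNs are inferred, and the low floor may have been deliberate.** The counts 12, 10 and 3 do depend on ULNs of 130 and 105. The internal inconsistency does not: no ULN fits either row. A deliberate change would have to be described in the SAP under Protocol Section 10, and it is not.

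**Conclusion.** The SAP's ALP limits are wrong as written. They contradict the protocol's multiples and, in the male row, leave values with no grade. At whole-number reporting and the implied ULNs, 22 values (12 male, 10 female) are over-graded as Mild and 3 male values lose a Grade 2.

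The conclusion that the rows are inconsistent needs no assumption about the ULN. The counts and replacement limits assume ULNs of 130 and 105, which the two upper limits in each sex give exactly, and they assume that 264 is the figure in the approved SAP. The total bilirubin and CPK points are secondary and have no effect at one decimal and at whole numbers respectively. The correction should be made, but nothing here shows a changed safety conclusion or a changed halting decision.

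**What to change.** Confirm the ULNs against the MOP reference ranges, then restate the rows from the Appendix B multiples with limits that meet. At the implied ULNs:

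- male ALP: 143-260 / >260-390 / >390;
- female ALP: 115.5-210 / >210-315 / >315;
- total bilirubin: 1.32-1.50 / >1.50-1.80 / >1.80;
- CPK Severe: >924 (male) and >576 (female).

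If the lower ALP Mild limit was intended, reconcile Table 4 with Appendix B and declare the departure in SAP Section 15. The male 261-263 gap has to be closed in either case.

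The cost is a check of the MOP ranges, a few corrected cells in one SAP table and the matching lines of the grading program. No data collection changes.
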